Association of Italian Hospital Gynecologists Obstetricians (AOGOI) declared contraindicated conditions to execute a delayed umbilical cord clamping:

Hypoxic-ischemic events: detachment of placenta, prolapse of the funiculus, uterine rupture, shoulder dystocia, premature rupture of fetal membranes, placenta previa, maternal collapse, embolism amniotic, maternal cardiac arrest. Monochorionic twins, Fetal Hydrops, Umbilical cord damaged, Isoimmunization Rh.

Researchers concluded that newborns subjected to Caesarean Section showed greater value of haemoglobin and lower value of red blood cells compared to newborns birth by vaginal delivery. Haematocrit difference was greater between newborns birth by elective Caesarean Section compared to those birth by Caesarean Section in labor (11). Nowadays, researchers found no side effects of delayed umbilical cord clamping except a slight increase of phototherapy needs (12).

Despite evidence of beneficial effects for delayed umbilical cord clamping after eutocic delivery, this practice is not yet taken into consideration after elective Caesarean Section. The aim of the study protocol is to investigate the effects of the clamping after 1 min from birth by elective Caesarean Section on heart rate, saturation, body temperature, bilirubin, haematocrit and glycemia.

2. Objective

Objective of the study was evaluating the effect of delayed clamping on FC, SpO₂, T, HGT, Ht and bilirubin in term newborns subjected to elective Caesarean Section

3. Study Location

- U.O.C. NICU-Neonatology – Department of mother and child’s Health
Poliambulanza Foundation, Brescia
- U.O. Gynecology ed Obstetrics - Villa Cinzia Clinic, struttura accreditata, Napoli

4. Population

46 term newborns (37-42 wks) subjected to Caesarean Section will be enrolled:

- 1. Group (A):** 23 newborns subjected to umbilical cord immediate clamping
- 2. Group (B):** 23 newborns subjected to umbilical cord delayed clamping

5. Inclusion Criteria

5.1 Mothers:

- Caesarean Section;
- BMI = 19-24,9;
- Age \leq 37 years

5.2 Newborns

- Gestational Age: 37 e 42 wks
- Birth Body Weight = Appropriate gestational age

6. Exclusion Criteria

6.1 Mothers

- Pathologies;
- Smoking mothers;
- Assumption of drugs during pregnancy
- Mother toxicomaniac

6.2 Newborn

- Admission in NICU;
 - Neonatal Resuscitation
- Hypoxic-ischemic events: detachment of placenta, prolapse of the funiculus, uterine rupture, shoulder dystocia, premature rupture of foetal membranes, placenta previa, maternal collapse, embolism amniotic, maternal cardiac arrest
 - Monochorionic twins
- Fetal Hydrops
- Umbilical cord damaged
- Isoimmunization Rh
- Respiratory and malformative diseases;
- Small for gestational age
- Large for gestational age
- Temperature $<36,5$ C
- Temperature $> 37,5$ C

· Acidosis

7. Procedure and Measurement

- Immediate umbilical cord clamping in the Group A
- Delayed umbilical cord clamping after 1 min from birth in Group B

In both groups will be evaluated:

○ **Saturation:**

Saturation will be detected at 5 min and 10 min from birth by oximeter Covidien, positioning the probe on right hand/wrist of the newborn. Reference value are: 80-85% at 5 min and 85-90% at 10 min (14);

○ **Heart Rate:**

Heart rate will be detected at 5 min and 10 min from birth by cardiomonitor. Reference value are 100-150 bpm (15)

○ **Temperature:** Temperature will be revealed at 5 min and 10 min from birth by Panda Warmer (GE), the probe of the infant radiant warmer. Reference value are 36,5-37,5 C

○ **Glycaemia:** HGT will be detected at 120 min from birth by capillary blood sampling of the heel. The sample will be analysed by “ABL90 Flex”

○ **Haematocrit:** Ht will be revealed at 120 min and 72 hrs from birth by capillary blood sampling of the heel. The sample will be analysed by “ABL90 Flex”

○ **Bilirubin:** Bilirubin will be detected after 72 hrs from birth by capillary blood sampling of the heel. The sample will be analysed by “ABL90 Flex”

8. Primary Outcome

H0: The case group will show the same values respect to control group for HR, SpO₂ and Temperature

H1: The case group will show different values respect to control group for HR, SpO₂ e Temperature

RegioneLombardia

9. Secondary Outcome

H0: The case group will show the same values respect to control group for HGT, bilirubin and Ht

H1: The case group will show different values respect to control group for HGT, bilirubin and Ht

10. Sample Size

Primary outcome will be analysed by ANOVA, repeated measures, between-within. Setting:

- **alfa error:** 5%
- **beta error:** 10%
- **Number of groups:** 2
- **Number of measurements:** 2
- **Correlation of repeated measures:** 0,5
- **Nonsphericity correlation:** 1
- **Effect size:** 0,25

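### Section 6.2 excludes newborns for events that can only follow assignment (NICU admission, resuscitation) and for untimed criteria that may do so, and no rule keeps randomised infants in the analysis

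*Combined protocol and SAP*

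**What the plan says.** Section 6.2 gives the newborn exclusion criteria. Among them are "Admission in NICU", "Neonatal Resuscitation", "Respiratory and malformative diseases", acidosis, "Temperature $<36,5$ C" and the matching upper limit of 37.5 C. None has a time of assessment. The same list contains "Small for gestational age" and its large-for-age counterpart, which mirror the inclusion criterion "Birth Body Weight = Appropriate gestational age" in Section 5.2.

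Section 7 has the cord clamped immediately in Group A and at 1 minute in Group B. It schedules newborn temperature at 5 and 10 minutes only and adds: "Reference value are 36,5-37,5 C". Those limits are the same as the exclusion limits. Section 8 makes temperature a primary outcome, with heart rate and saturation.

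Section 10 plans a between-within repeated-measures ANOVA and 46 newborns, 23 per group. Section 11 calls the trial randomised and open, with allocation by software, and does not say when allocation happens. The visible text defines no analysis population and has no rule for an infant who meets an exclusion after assignment.

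**The concern.** An exclusion criterion protects a randomised comparison only if it is settled before assignment. One that is settled afterwards selects on events the intervention may influence, and the groups analysed need no longer be the groups randomised. Resuscitation, NICU admission and respiratory disease belong to the same transition at birth that the trial studies, so they are possible effects of when the cord is clamped. Because the trial is open, whoever applies the criteria can know the arm.

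Temperature raises a further problem. If the criterion is applied to the scheduled readings, infants are removed because of their value on a primary outcome. Neither Section 8 nor Section 9 lists the excluded events as outcomes, so without counts by arm a reader could not tell whether an imbalance had arisen.

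**Working it through.** **1. Order of events.** Group A's immediate clamping (Section 7) requires the assignment to exist at birth, although Section 11 gives no time for it. Resuscitation of the newborn and NICU admission cannot precede birth. These two criteria therefore follow assignment in every case. Respiratory disease, acidosis and temperature carry no time; they may be established after birth, but the text does not settle it. Malformations may be known before birth, and the argument does not rely on them.

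**2. The plan's own sample size.** Inputs from Section 10: f = 0.25, two groups, m = 2 measurements, correlation rho = 0.5, nonsphericity 1, alpha 5%, beta 10%. For the group-by-time interaction, lambda = f² × N × m / (1 − rho).
- N = 46: lambda = 0.0625 × 46 × 2 / 0.5 = 11.5; on 1 and 44 degrees of freedom, power is 0.912.
- N = 44: lambda = 11.0; power is 0.8997, just short of 90%.

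So 46 is reproduced as the smallest even total for the interaction test, with no allowance for infants removed after assignment.

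**3. Temperature, if the limits are applied to the scheduled readings.** The documents give no temperature mean or SD, so these are assumptions: normal readings, equal SDs in both arms, true means of 37.0 and 36.8 C at both times, and SD of 0.2, 0.3 or 0.4 C. The correlation of 0.5 is Section 10's.

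For removal on a single reading, the mean of those kept is mu + SD × [φ(a) − φ(b)] / [Φ(b) − Φ(a)], where a = (36.5 − mu)/SD and b = (37.5 − mu)/SD. At SD 0.3:
- mu = 37.0: the limits are symmetric, so the mean stays at 37.000.
- mu = 36.8: a = −1.000 and b = 2.333. The mean becomes 36.8 + 0.3 × (0.2420 − 0.0262)/(0.9902 − 0.1587) = 36.878.
- The 0.20 C difference becomes 0.122 C.

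For removal when either reading is out of range, the bivariate normal density is integrated over the square from 36.5 to 37.5 C:

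| SD (C) | Removed, mean 37.0 | Removed, mean 36.8 | Removed overall | Difference left (true 0.20 C) |
|---|---|---|---|---|
| 0.2 | 2.3% | 11.6% | 7% | 0.165 C |
| 0.3 | 16.8% | 27.3% | 22% | 0.107 C |
| 0.4 | 35.1% | 41.9% | 38% | 0.067 C |

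Removal is unequal between arms, and the difference shrinks in each of these cases.

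**4. Effect on the interaction.** When each arm's mean is the same at 5 and 10 minutes, as above, the truncation bias is equal at both times and the interaction is unbiased. This fails once means change over time. With a constant 0.20 C arm difference and an assumed common fall of 0.3 C (37.1 then 36.8 against 36.9 then 36.6), truncation creates an interaction of about 0.03, 0.02 or 0.01 C at the three SDs, where the true value is zero. If a 0.20 C difference arises only between the readings (37.0 then 37.0 against 37.0 then 36.8), the true interaction of 0.20 C becomes 0.186, 0.154 or 0.120 C.

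**The case against.** The protocol evidently means to study transition in healthy term newborns, and these criteria describe that population. It never says that an assigned infant will be dropped from the analysis. In such a low-risk group, resuscitation and NICU admission may be rare. The figures above concern temperature, the criterion whose timing is least certain, and they rest on assumed means and SDs.

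Much of this stands, and it limits the point. A reader might infer any of the following, and the documents do not support them:

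- **The plan certainly truncates a primary outcome.** No section ties the temperature exclusion to the 5- and 10-minute readings. They are the only newborn temperatures scheduled, which makes that reading natural but not established.
- **The 46 would shrink by the percentages shown.** Section 10 says 46 will be enrolled. It does not say whether that number is counted before exclusions, or whether excluded infants are replaced. Replacement would protect the count but not the comparison.
- **Truncation would create or reverse a temperature effect.** That is possible with unequal SDs: with assumed SDs of 0.2 and 0.4 C, equal means of 36.7 C and removal on one reading, a spurious 0.12 C appears. Nothing in the documents suggests such a ratio.
- **The birth-weight criteria are the same fault.** Weight is confirmed only at delivery, so an assigned infant may be found ineligible, but clamping does not determine whether an infant is small or large for gestational age.

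The intended population does not answer the core point. Two listed criteria cannot be applied before assignment, and nothing visible keeps infants who meet them in the analysis.

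**Conclusion.** The concern holds in a limited form. It is certain that NICU admission and resuscitation are exclusions that follow assignment, and that the visible text supplies no time of randomisation, analysis set or retention rule. It follows that randomised infants can be removed or replaced for possible effects of clamping, in an open trial; it does not follow that they will be.

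The documents give no event rates and no temperature mean or SD, so the actual size and direction of bias cannot be determined. For heart rate and saturation it is probably small, a judgement that rests on such events being few in this population. For temperature the loss could be large: under the equal-SD assumptions and removal on either reading, between about 18% (0.035/0.20) and 66% (0.133/0.20) of a 0.20 C difference disappears, but only if the criterion uses the outcome readings. The group-by-time interaction on which 46 is based is free of this bias only when arm means are constant from 5 to 10 minutes; with a constant arm difference and common cooling, the bias is not zero but small. This should be corrected, with medium confidence in its practical importance.

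**What to change.** - State in Section 11 that randomisation precedes delivery, and apply as eligibility criteria only conditions established before assignment.
- Define the primary analysis set as all randomised infants, in the assigned group, with every available 5- and 10-minute value. Include infants found at or after birth to meet a Section 5.2 or 6.2 criterion.
- Do not use a temperature taken after birth to exclude an infant from the primary analysis.
- Report NICU admission, resuscitation, respiratory disease and any recorded acidosis by arm, descriptively.
- As a sensitivity analysis, repeat the analysis without infants who were resuscitated, were admitted to NICU, or had respiratory disease or acidosis, with no temperature restriction.
- Leave the contraindications to delayed clamping listed in the introduction, and their clinical handling, unchanged.

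The cost is rewording of Sections 5.2, 6.2 and 11, a statement of the analysis set, one table by arm and one repeated analysis. No new heart rate, saturation or temperature measurement is needed, and acidosis is reported only where it was recorded. The downside is a change in the question: the primary analysis would address all randomised infants and not only those who stayed healthy, with somewhat more variable early values and a few missing ones.
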